7.2.5. Clinical Outcomes of Interest

The Roctavian Cohort and SoC Cohort in this study will be compared regarding the clinical outcomes of bleeds, use of hemostatic treatments, and assessments of joint health, quality of life and pain. See Section 10.3 and the SAP for further detail on the planned comparisons. These clinical outcomes will be derived from data entered in the DHR at or after the index date during the follow-up period.

7.2.5.1. Bleeding events

The primary endpoint, as well as endpoints for secondary objectives regarding bleeding events, will be based on bleeding events recorded in the DHR. Categories of bleeding events, along with relevant variables collected in the DHR, are described in [Table 6](#). Bleeding events will be compared regarding both annualized bleeding rates (ABRs), which allow for calculation based on variable amounts of time, and the proportion of participants with zero bleeds over a fixed period of time (eg, 1-year increments, among those with 2 years of follow-up, and/or among those with the full 3 years of follow-up for the AbD). Details on the calculation of these outcomes based on the bleeding events recorded in the DHR are described further in [Section 10.3](#) and the SAP, including counting of events recorded on consecutive days. Bleeding events of a specific severity or occurring in a specific location (eg, a joint) are based upon the discretion of the physician recording the data in the DHR. Bleeding events will be recorded from the index date through the follow-up period for each participant in the AbD.

Table 6: Bleeding Events

Variable	Description	Captured in DHR	Time period for Analysis	Entry into DHR	Operational notes including Relevant Data Fields in DHR
Treated Bleeds	Bleeding events requiring treatment with FVIII	✓	Follow-up	Ongoing	Derived based on therapy usage recorded in the DHR for spontaneous bleeding (regardless of severity).
Major bleeds	Severe or life-threatening bleeds	✓	Follow-up	Ongoing	Treated bleeds (see above), but with severity recorded as 'severe' or 'life-threatening' in the DHR. Major bleeds will be a sub-set of treated bleeds. Definition of 'severe' and 'life-threatening' severity will be consistent with existing practices in the DHR ¹ .
Life-threatening bleeds	Life-threatening bleeding events	✓	Follow-up	Ongoing	Treated bleeds (see above) with severity recorded as 'life-threatening' in the DHR. Life-threatening bleeds will be a sub-set of treated bleeds and major bleeds. Definition of 'life-threatening' severity will be consistent with existing practices in the DHR ¹ .

Variable	Description	Captured in DHR	Time period for Analysis	Entry into DHR	Operational notes including Relevant Data Fields in DHR
Joint bleeds	Bleeds occurring in a joint or target joint	✓	Follow-up	Ongoing	Treated bleeds (see above) regardless of severity, but with a location/localization of 'joint' or 'target joint' in the DHR. Major bleeds will be a sub-set of treated bleeds.

DHR, German Hemophilia Register; FVIII, Coagulation factor VIII

¹ Definition confirmed by DHR as consistent with PedNet. A bleed is classified as severe if the bleed causes pain, swelling, and/or mobility disability and does not end within 24 hours. A bleed is classified as life threatening if the bleed is severe (causes pain, swelling, and/or mobility disability and does not end within 24 hours) and poses a special risk to the patient.

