4. STUDY OBJECTIVES AND ENDPOINTS

The aim of this non-interventional study is to evaluate the overall effectiveness and safety of Roctavian compared to SoC hemostatic prophylaxis treatments for PwSHA.

The specific objectives are listed below. All objectives will compare Roctavian and SoC with exogenous FVIII or emicizumab, unless otherwise noted.

Table 1: Objectives and Endpoints

[figure not shown]
Objectives	Endpoints
Primary	
To compare the annualized bleeding rate for treated bleeds.	
 Bleeding events requiring treatment with exogenous FVIII
Secondary	
To compare the annualized bleeding rate for major, life threatening, and joint bleeds.	
 Major bleeding events Life-threatening bleeding events Bleeding events occurring in the joint
To compare the proportion of people with zero bleeds for treated, major, life threatening, and joint bleeds.	
 Bleeding events requiring treatment with exogenous FVIII Major bleeding events Life-threatening bleeding events Bleeding events occurring in the joint
To compare the use of hemostatic medications.	
 Prophylactic hemostatic treatments On-demand hemostatic treatments
To compare joint health, quality of life, and pain.	
 Hemophilia Quality of Life assessment (Haemo-QoL-A) Hemophilia Joint Health Score (HJHS) Brief Pain Inventory-Short Form (BPI-SF)
To compare safety events of interest.	
 All cause death Hemophilia-related death Adverse events leading to hospitalization or death Targeted adverse events of development of FVIII inhibitors, thromboembolic events, new malignant neoplasms, and severe liver disease (liver failure or cirrhosis)
To describe time to resumption of prophylactic treatment among persons administered Roctavian.	
 Resumption of prophylactic hemostatic treatments

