Bleeding History					
Bleeding history	Bleeding events in the 12 months prior to index	✓	Baseline	Ongoing	
Description of cohorts based in annualized bleeding rates.
 
See Table 6 for further description of bleed types recorded in the DHR. Derived based on therapy usage recorded in the DHR for suspected, spontaneous, traumatic, or unknown cause of bleeding.

Variable	Description	Captured in DHR	Time period for Analysis	Entry into DHR	Operational notes including Relevant Data Fields in DHR
Treatment History					
Use of prophylaxis	Hemostatic prophylaxis use prior to index	✓	Baseline	Ongoing	Derived based on the therapy usage recorded in the DHR. Inclusion criteria confirmed at time of enrollment based on DHR field confirming that the participant fulfills the AbD inclusion/exclusion criteria.
Prophylaxis type	Medication class utilized for prophylaxis	✓	Baseline	Ongoing	Description of cohorts. Derived based on the therapy usage recorded in the DHR for 'prophylaxis'. Including (but not limited to) description of the use of: FVIII only (any, standard half-life (SHL) products only, extended half-life (EHL) products only, SHL & EHL) Non-factor products only (eg, emicizumab) FVIII and non-factor products
FVIII Consumption	Total FVIII consumption during the 12 months prior to index	✓	Baseline	Ongoing	Description of cohorts. Derived based on reported FVIII consumption for each therapeutic use of FVIII, reported for different prophylaxis types. Will be described based on total FVIII utilized in international units (IUs), as well as IU/kg based on availability of weight data (see note in Table 3).
Infusion Rate	Number of infusions during the 12 months prior to index	✓	Baseline	Ongoing	Description of cohorts. Providing data allows, derived based on the therapy usage and frequency of during individual usage periods recorded in the DHR for any reason. Data is expected to be able to allow for summaries of annualized infusion/injection rate (AIR).

Variable	Description	Captured in DHR	Time period for Analysis	Entry into DHR	Operational notes including Relevant Data Fields in DHR
AAV Status					
AAV Antibody testing	Serostatus for AAV 5 antibodies	✓	Index	At/around time of administration for Roctavian Cohort Ongoing for any testing done during the study	Derived from AAV testing for AAV5 being conducted and result of positive/negative.
Comorbidities					

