7.4.3. Outcome Variables

Primary and secondary outcomes specific to each objective are outlined in Table 5 below. Note, all outcomes described below are collected from the index date in both study Cohorts.

Table 5: Outcome Variables

Variable	Captured in DHR	DHR data field name(s)	Operational definition and calculation of outcome measures	Timepoints for data collection
Bleeding Events				
Treated ABR	Yes (calculated)	
 Therapy scheme Occasion Date of bleed Therapy start End of therapy 	
 Number of treated bleeding events per year Calculate ABR using number of treated bleed events within the relevant time period (≥ 1 year of follow-up, ≥ 2 years of follow-up, ≥ 3 years of follow-up, all available follow-up) 
 A bleeding event is captured if occasion for therapy is spontaneous bleeding/hemorrhage (regardless of severity) Bleeds will be identified as treated bleeds if they meet one of the following criteria: 
 If bleed date is within 3 calendar days of treatment date where occasion for treatment is one of the hemorrhage values OR therapy scheme is "on demand" If multiple bleeds with different localization occur on the same calendar day of the last bleed before treatment for bleed, the subsequent treatment within 3 calendar days is considered to pair with each of these bleeds; Each of these bleeds that is within 3 calendar days of the subsequent treatment is therefore considered to be a treated bleed Two bleeds of the same localization are considered to be one bleed if the second occurs within 3 calendar days from the date of the last treatment for the first bleed; The last treatment is defined as the last treatment before a new bleed occurs, either in the same or in a different location regardless of whether the second bleed is followed by a treatment 	
 ≥ 1 year ≥ 2 years ≥ 3 years All available follow-up

Variable	Captured in DHR	DHR data field name(s)	Operational definition and calculation of outcome measures	Timepoints for data collection
			
 Calculate annualized metric of the number of bleeding events by dividing the number of bleeds by the number of days in the relevant time period, multiplied by 365.25 	

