- Each prophylaxis-specific subgroup will be described and compared to the Roctavian Cohort separately as sample size permits.

- A likelihood ratio test will be applied to examine if the SoC treatment types are statistically significantly different.

Age Group Subgroup Analysis

- Participants in both Roctavian and SoC Cohorts will be stratified on age at index date in the following groupings: 18-40, 41-64, 65+.
- A likelihood ratio test will be applied to examine if age groups are statistically significant different across the primary and secondary objective results.

AAV5 Antibody Status Subgroup Analysis

- The study results will be stratified by participants with known AAV5 antibody status at study consent (presence) versus those with no known AAV5 antibody status (absence).
- Missing AAV5 status will be categorized as absence. See Table 3 for operationalization of the AAV5 variable.
- Note, the ability to conduct this subgroup analysis is dependent upon the availability of the AAV5 testing in clinical practice among the SOC cohort.

SoC Switching Sensitivity Analysis

- The study results will be reported for participants in the SoC Cohort who receive Roctavian during the follow-up period and are censored at the time of switching.

Traumatic Bleeds Sensitivity Analysis

If >10% of the population experiences traumatic bleeds as indicated in the DHR (occasion = “traumatic hemorrhage”), a sensitivity analysis will be conducted to compare the ABRs of those with traumatic bleeds as compared to the overall Cohorts (occasion = “spontaneous hemorrhage”).

Switching Sensitivity Analyses

If >15% of the SoC Cohort switches classes of treatment (SHL, EHL, PD, emicizumab) during the follow-up period or if a specific class switching pattern occurs in >10% of the population, a sensitivity analysis will be conducted of participants who remain on the same class for the duration of the follow-up period. ABRs will be calculated for this population that do not switch FVIII classes to understand how this differs from the ABRs for the overall SoC Cohort.

COA measures (as described in Section 7.9.4.4) will be described for participants in the SoC Cohort who stay on the same class of treatment throughout the duration of the follow-up period.

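### Treated bleeds are named without regard to cause but counted only when spontaneous, and the baseline bleeding rate has two conflicting definitions

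*Protocol*

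**What the plan says.** **Endpoint as named.** Protocol Section 4, Table 1 (and the synopsis) gives the primary endpoint as "Bleeding events requiring treatment with exogenous FVIII". No cause is mentioned.

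**Endpoint as counted.** Table 6 in protocol Section 7.2.5.1 repeats that description and then gives the operational rule: "Derived based on therapy usage recorded in the DHR for spontaneous bleeding (regardless of severity". SAP Table 5 agrees: "A bleeding event is captured if occasion for therapy is spontaneous bleeding/hemorrhage (regardless of severity". SAP Section 7.9.3 restates it for the primary analysis.

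**Outcomes built on it.** In Table 6, "Major bleeds will be a sub-set of treated bleeds" and "Life-threatening bleeds will be a sub-set of treated bleeds and major bleeds". Joint bleeds are "Treated bleeds (see above) regardless of severity, but with a location/localization of 'joint' or 'target joint' in the DHR". Protocol Section 10.3.7.2 takes the zero-bleed proportions from the same Table 6 outcomes.

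**Baseline.** Protocol Table 4 defines bleeding history more widely: "Derived based on therapy usage recorded in the DHR for suspected, spontaneous, traumatic, or unknown cause of bleeding". SAP Table 3 derives prior ABR from spontaneous bleeds only. Protocol Section 10.3.3.1 and Table 9 put prior ABR into the propensity score whatever its statistical association. No other covariate has that status.

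**Traumatic bleeds.** SAP Section 7.9.5 plans a sensitivity analysis only if more than 10% of the population has traumatic bleeds. It is to "compare the ABRs of those with traumatic bleeds as compared to the overall Cohorts".

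**The concern.** A reader of the results will take treated, major and life-threatening bleeds to mean what the objectives table says. Under the operational rule they mean something narrower, and neither document gives a reason. The zero-bleed outcomes are the most exposed, because one uncounted event moves a participant into the bleed-free group. Protocol Section 10.1 itself names freedom from bleeding as a goal of treatment.

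The baseline conflict is separate. Prior ABR is the most important adjustment variable in a non-randomized comparison, and two programmers working from the two tables would build two different propensity scores.

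The planning ABRs are described as rates of treated bleeds with no cause stated, so it is also unclear whether the study was sized for the quantity it will count.

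**Working it through.** **1. Which causes count where**

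| Quantity | Spontaneous | Traumatic | Unknown cause | Suspected |
|---|---|---|---|---|
| Primary endpoint as named (protocol Table 1) | yes | yes | yes | not addressed |
| Treated bleeds as derived (protocol Table 6; SAP Table 5, 7.9.3) | yes | no | no | no |
| Major, life-threatening, joint, zero-bleed (protocol Table 6, 10.3.7.2) | yes | no | no | no |
| Baseline history (protocol Table 4) | yes | yes | yes | yes |
| Prior ABR (SAP Table 3) | yes | no | no | no |
| On-demand FVIII use (protocol Table 7, SAP Table 5) | yes | yes | not listed | yes |

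The register can separate the causes, since Tables 4 and 7 use them. The restriction is therefore not forced by the data source.

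**2. One participant followed through the rules.** Take a participant whose only bleed in follow-up is traumatic, treated with FVIII and recorded as life-threatening. He fails the spontaneous condition, so he has no treated bleed. Major and life-threatening bleeds are subsets of treated bleeds, so he has none of those. He is reported as having zero treated, zero major and zero life-threatening bleeds. The FVIII he received does count as on-demand use.

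**3. The plan's sample size.** Inputs from protocol Section 10.1 and SAP Section 7.6: SoC rate 3, Roctavian rate 0.85, null ratio 0.5, allocation 0.2, one year of exposure, overdispersion 1.5, one-sided 2.5%, power 80%.

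- V1 = 1/3 + 1/(0.2 × 0.85) + 1.2 × 1.5/0.2 = 15.216
- V0 = (1 + 0.5 × 0.2)² / [0.5 × 0.2 × (3 + 0.2 × 0.85)] + 9 = 12.817
- N(SoC) = (1.960 × √12.817 + 0.842 × √15.216)² / (ln 0.5 − ln 0.283)² = 328.8, so 329 SoC and 66 Roctavian, 395 in all

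The plan states 330 + 67 = 397, which agrees to within rounding. The arithmetic is sound. What is missing is the definition of bleed behind the 3 and the 0.85.

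**4. Why no size follows.** There are two readings of those rates, both illustrations on assumptions that the documents do not supply.

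- *The rates cover all causes.* Assume a share s is spontaneous in both cohorts, with the ratio held at 0.283 and overdispersion at 1.5. Replacing the rates by 3s and 0.85s gives a required total of 411, 452 and 527 for s = 0.9, 0.7 and 0.5. Power at 330/66 is 78.8%, 75.1% and 69.2%, against 80.1% at s = 1.
- *The rates are spontaneous only.* Assume the same traumatic rate t in both cohorts. The all-cause ratio is (0.85 + t)/(3 + t), which is 0.338, 0.386 and 0.463 for t = 0.25, 0.5 and 1.0, against 0.283 at t = 0. The absolute difference is 3 − 0.85 = 2.15 for every t.

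**The case against.** Spontaneous-only is applied consistently across the outcome definitions, so it looks like a choice and not a slip, and it has something to recommend it. Traumatic bleeds depend partly on sport and activity, which protocol Section 10.5 says the registry cannot capture. The same section warns that sites differ in giving FVIII for suspected bleeds that may be joint pain. These are fair reasons to keep suspected bleeds out of the primary count and to report a spontaneous-only analysis. They do not justify calling the result treated bleeds without qualification.

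Several stronger readings are tempting and are not supported.

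- *Traumatic bleeds disappear from the study.* They do not. They count in on-demand FVIII use, and the use of treatment for bleeds or short-term prophylaxis is itself compared (protocol Section 10.3.7.3, SAP Section 7.9.4.3). A bleed recorded as a medically relevant event leading to hospitalization or death can also enter the safety outcomes (protocol Table 8).
- *The propensity score uses a different definition from the outcome.* This is not settled. Protocol Section 10.3.3 draws candidate variables from Table 4, but Section 10.3.3.1 refers to the SAP for their operational form, and SAP Table 3 matches the outcome. Table 4 labels its entry as descriptive. The finding is an unresolved conflict.
- *The SAP's traumatic-bleed analysis cannot compare Roctavian with SoC.* Its sentence describes another contrast, but SAP Section 7.9.5 invokes the same methods as the main analyses, and Annex 12.1 extends the two-cohort table shells to the sensitivity analyses. The wording is poor; its intent is uncertain.
- *SAP Table 5 contradicts itself* by pairing bleeds with treatments for any hemorrhage value. This can be read as two steps, capture of a spontaneous bleed and then pairing with a treatment, so it is at most ambiguous.
- *Unblinded attribution of cause drives the result.* This is possible, but it is inference. Section 7.2.5.1 assigns severity and location to the physician's discretion and does not say who judges cause.

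**Conclusion.** The point holds as an inconsistency of definition. The named primary endpoint includes FVIII-treated traumatic bleeds and the counted one does not. The gap carries into every ABR and zero-bleed outcome. The definition of the one compulsory propensity-score covariate differs between protocol Table 4 and SAP Table 3. These conclusions rest on the text alone.

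No magnitude can be given, because the documents report no split of bleeds by cause. A reader might infer from the illustrations that an all-cause rate ratio would drift close to 0.5. That needs spontaneous-only planning rates and an equal traumatic rate in both cohorts, and neither is stated. At t = 1.0 traumatic bleeds would outnumber spontaneous ones in the Roctavian Cohort (1.0 against 0.85). The 0.5 threshold belongs to the test in SAP Section 7.9.3; protocol Section 10.1 says the nulls actually tested are not shifted. The protocol's own primary comparison (Section 10.3.6.1) is the absolute difference, which would stay at 2.15 under that assumption. The power figures are likewise conditional on an assumed share and on one year of exposure.

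The plan should be corrected before the SAP is finalized, which protocol Section 10.3 places ahead of the first data cut.

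**What to change.** 1. In protocol Table 6 and SAP Table 5, with SAP Section 7.9.3, derive treated bleeds as FVIII-treated bleeds of spontaneous, traumatic or unknown cause, to match the named endpoint.
2. Apply the same rule to major, life-threatening, joint and zero-bleed outcomes and to baseline ABR, so that protocol Table 4 and SAP Table 3 agree.
3. Replace the 10% trigger in SAP Section 7.9.5 with unconditional IPTW comparisons of Roctavian with SoC for (a) spontaneous bleeds only and (b) bleeds including suspected ones.
4. If the sponsor keeps spontaneous-only as primary, rename the endpoints as treated spontaneous bleeds throughout and make the all-cause weighted comparison the unconditional sensitivity analysis.
5. State which definition the planning ABRs of 3 and 0.85 refer to.

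The cost is wording and some programming, since the occasion codes are already in the register. The rate ratio may look less favourable, and traumatic bleeds bring in variation from physical activity that the registry does not record. The spontaneous-only analysis in step 3 lets readers judge how much that matters.

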7.2.5.2. Use of hemostatic treatments

Endpoints for secondary objectives regarding hemostatic therapy usage will be based on therapeutic usage of exogenous FVIII and emicizumab recorded in the DHR. Key endpoints for comparing use of hemostatic therapy, along with relevant variables collected in the DHR, are described in [Table 7](#). Use of any exogenous FVIII or emicizumab, the number of uses (stratified by prophylaxis vs on-demand/for bleed treatment), amount of exogenous FVIII consumed and number of infusions will be compared between cohorts. Endpoints will be compared based on the total follow-up, as well as specific periods of time starting from index date (eg, during the 2nd or 3rd year of follow-up). Details on the calculation of these outcomes based on the therapeutic usage recorded in the DHR are described further in [Section 10.3](#) and the SAP. Hemostatic therapy usage will be recorded from the index date through the follow-up period for each participant in the AbD.

For the Roctavian Cohort only, the proportion of participants who return to prophylactic hemostatic therapy, along with the time to return to prophylaxis will be described for those in the cohort who ended prophylaxis post Roctavian administration.

Table 7: Hemostatic Treatment During Follow-Up

Variable	Description	Captured in DHR	Time period for Analysis	Entry into DHR	Operational notes including Relevant Data Fields in DHR
Use of hemostatic treatments	Use of any hemostatic treatments	✓	Follow-up	Ongoing	Derived based on therapy usage recorded in the DHR for exogenous FVIII and/or emicizumab.
FVIII Consumption	FVIII consumption during follow-up	✓	Follow-up	Ongoing	Derived based on reported FVIII consumption for each therapeutic use of FVIII, reported for different prophylaxis types (see Table 4) and on-demand use. Will be described based on total FVIII utilized in international units (IUs), as well as IU/KG based on weight data (see Table 3). On demand use of FVIII will be defined as use of FVIII for suspected bleeding, spontaneous bleeding, traumatic, bleeding/bleeding, or intensified on-demand treatment (short-term prophylaxis).
Infusion/ Injection Rate	Number of infusions/ injections during follow-up	✓	Follow-up	Ongoing	Derived based on the therapy usage and frequency of use during individual usage periods recorded in the DHR for any reason and summarized as annualized infusion/injection rate (AIR).
Return to prophylaxis	*For Roctavian Cohort only* Use of continuous prophylaxis	✓	Follow-up	Ongoing	Derived based on the recording of physician report of 'return to prophylaxis' in the DHR.

AIR, annualized infusion/injection rate; DHR, German Hemophilia Register; FVIII, Coagulation factor VIII; SAP, Statistical Analysis Plan.

